8.2.1 Adverse Events

Adverse events will be coded according to pre-specified Tactile internal codes. Adverse events will be summarized by severity, outcome, causality and seriousness (i.e., SAE) and stratified by treatment group (Table 14.3.1). For subjects with more than one event, the event with the highest level of severity, outcome or causality, seriousness, respectively, will be reported. The number and percentage of subjects with an event by the internal Tactile AE codes will be compared by treatment group (Tables 14.3.2). Subjects with more than one event by internal Tactile code will be counted only once. All AEs will be listed, sorted by treatment group, subject identification, and date of the AE (Table 16.2.7.1). Data presented will include: causality, severity, seriousness, outcome, verbatim description, internal Tactile codes.

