APPENDIX: DATA TABLES

TACTILE TABLES - SAP

Sponsor: Tactile Medical Systems
Protocol: 6010

page 1 of x

Table 14.1.1 Patient Disposition

ITT sample

	1.5cm<=size<=12cm				12cm<size<= 50cm			
	1<=age<6 months		1<=age<6 months		6<=age<=24 months		6<=age<= 24 months	
	Treatment (N)	Control (N)	Treatment (N)	Control (N)	Treatment (N)	Control (N)	Treatment (N)	Control (N)
Randomized	xx/xx(xxx.x%)	xx/xx(xxx.x%)	xx/xx(xxx.x%)	xx/xx(xxx.x%)	xx/xx(xxx.x%)	xx/xx(xxx.x%)	xx/xx(xxx.x%)	xx/xx(xxx.x%)
Safety	xx/xx(xxx.x%)	xx/xx(xxx.x%)	xx/xx(xxx.x%)	xx/xx(xxx.x%)	xx/xx(xxx.x%)	xx/xx(xxx.x%)	xx/xx(xxx.x%)	xx/xx(xxx.x%)
Completed	xx/xx(xxx.x%)	xx/xx(xxx.x%)	xx/xx(xxx.x%)	xx/xx(xxx.x%)	xx/xx(xxx.x%)	xx/xx(xxx.x%)	xx/xx(xxx.x%)	xx/xx(xxx.x%)
Discontinued	xx/xx(xxx.x%)	xx/xx(xxx.x%)	xx/xx(xxx.x%)	xx/xx(xxx.x%)	xx/xx(xxx.x%)	xx/xx(xxx.x%)	xx/xx(xxx.x%)	xx/xx(xxx.x%)
Primary Reason for Discontinuation:								
Adverse Event	xx/xx(xxx.x%)	xx/xx(xxx.x%)	xx/xx(xxx.x%)	xx/xx(xxx.x%)	xx/xx(xxx.x%)	xx/xx(xxx.x%)	xx/xx(xxx.x%)	xx/xx(xxx.x%)
Protocol Violation	xx/xx(xxx.x%)	xx/xx(xxx.x%)	xx/xx(xxx.x%)	xx/xx(xxx.x%)	xx/xx(xxx.x%)	xx/xx(xxx.x%)	xx/xx(xxx.x%)	xx/xx(xxx.x%)
Lost to Follow-up	xx/xx(xxx.x%)	xx/xx(xxx.x%)	xx/xx(xxx.x%)	xx/xx(xxx.x%)	xx/xx(xxx.x%)	xx/xx(xxx.x%)	xx/xx(xxx.x%)	xx/xx(xxx.x%)
Other	xx/xx(xxx.x%)	xx/xx(xxx.x%)	xx/xx(xxx.x%)	xx/xx(xxx.x%)	xx/xx(xxx.x%)	xx/xx(xxx.x%)	xx/xx(xxx.x%)	xx/xx(xxx.x%)

TACTILE TABLES - SAP

Sponsor: Tactile Medical Systems
 Protocol: 6010

page 1 of x

Table 14.1.2 Patient Disposition By Site
 ITT sample

	Treatment N(%) ^b	Control N(%) ^b	Total N(%) ^b
xxxx	xx/xx(xxx.x%)	xx/xx(xxx.x%)	xx/xx(xxx.x%)
xxxx	xx/xx(xxx.x%)	xx/xx(xxx.x%)	xx/xx(xxx.x%)
xxxx	xx/xx(xxx.x%)	xx/xx(xxx.x%)	xx/xx(xxx.x%)
xxxx	xx/xx(xxx.x%)	xx/xx(xxx.x%)	xx/xx(xxx.x%)
xxxx	xx/xx(xxx.x%)	xx/xx(xxx.x%)	xx/xx(xxx.x%)

Note: denominator of all percentages is number randomized by group

TACTILE TABLES - SAP

Sponsor: Tactile Medical Systems
Protocol: 6010

page 1 of Y

Table 14.3.1 Safety Analysis: Summary Incidence of Adverse Events
Safety sample

Condition	Treatment N(%)	Control N(%)	P-value
Safety Analysis Set	xx	xx	
Patients with Adverse Events	xx(xxx.x%)	xx(xxx.x%)	x.xxx
Patients with AEs by Severity ^a			
No Event	xx(xxx.x%)	xx(xxx.x%)	x.xxx
Mild	xx(xxx.x%)	xx(xxx.x%)	
Moderate	xx(xxx.x%)	xx(xxx.x%)	
Severe	xx(xxx.x%)	xx(xxx.x%)	
Patients with AEs by Causality ^a			
Definitely related	xx(xxx.x%)	xx(xxx.x%)	x.xxx
Probably related	xx(xxx.x%)	xx(xxx.x%)	

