Possibly related	xx(xxx.x%)	xx(xxx.x%)	
Not related	xx(xxx.x%)	xx(xxx.x%)	
No Event	xx(xxx.x%)	xx(xxx.x%)	
Outcome			
No Event	xx(xxx.x%)	xx(xxx.x%)	x.xxx
Resolved	xx(xxx.x%)	xx(xxx.x%)	
Resolved w/ sequelae	xx(xxx.x%)	xx(xxx.x%)	
Continuing	xx(xxx.x%)	xx(xxx.x%)	
Lost to follow-up	xx(xxx.x%)	xx(xxx.x%)	
Death	xx(xxx.x%)	xx(xxx.x%)	

TACTILE TABLES - SAP

Condition	Treatment N(%)	Control N(%)	P-value
Patients with SAEs	xx(xxx.x%)	xx(xxx.x%)	x.xxx
Patients Discontinued due to AE	xx(xxx.x%)	xx(xxx.x%)	x.xxx

NOTE: P-value based on Kruskal-Wallis test controlling for stratification. Denominator is the number of patients in the Safety Analysis Set.
^aPatients experiencing more than one adverse event are counted under the maximum severity experienced across events.

TACTILE TABLES - SAP

Sponsor: Tactile Medical Systems
 Protocol: 6010

page 1 of Y

Table 14.3.2 Safety Analysis: Incidence of Adverse Events by Internal AE Code
 Safety sample

Internal AE Code	Treatment N(%)	Control N(%)	p-value ^a
Patients with Adverse Events	xx(xxx.x%)	xx(xxx.x%)	xxxx
AE_CODE XX	xx(xxx.x%)	xx(xxx.x%)	x.xxx
AE_CODE XX	xx(xxx.x%)	xx(xxx.x%)	x.xxx
AE_CODE XX	xx(xxx.x%)	xx(xxx.x%)	x.xxx
AE_CODE XX	xx(xxx.x%)	xx(xxx.x%)	x.xxx
AE_CODE XX	xx(xxx.x%)	xx(xxx.x%)	x.xxx
AE_CODE XX	xx(xxx.x%)	xx(xxx.x%)	x.xxx
AE_CODE XX	xx(xxx.x%)	xx(xxx.x%)	x.xxx
AE_CODE XX	xx(xxx.x%)	xx(xxx.x%)	x.xxx
AE_CODE XX	xx(xxx.x%)	xx(xxx.x%)	x.xxx
AE_CODE XX	xx(xxx.x%)	xx(xxx.x%)	x.xxx

Note: A patient experiencing multiple incidences of an event with the same internal AE code is counted only once.
^a P-value calculated from CMH Test.

TACTILE TABLES - SAP

Sponsor: Tactile Medical Systems
 Protocol: 6010

page 1 of Y

Table 16.2.7.1 Listing of Adverse Events
 Safety sample

Treatment Group	Patient ID	Onset Date (Study Day)	Stop Date (Study Day)	Internal AE Code	Serious	Duration	Severity	Causality	Outcome
xxx	xx	ddmmyy (xx)	ddmmyy(xx)	xx	xx	xx	xx	xx	xx
xxx	xx	ddmmyy (xx)	ddmmyy(xx)	xx	xx	xx	xx	xx	xx
xxx	xx	ddmmyy(xx)	ddmmyy(xx)	xx	xx	xx	xx	xx	xx
xxx	xx	ddmmyy(xx)	ddmmyy(xx)	xx	xx	xx	xx	xx	xx
xxx	xx	ddmmyy(xx)	ddmmyy(xx)	xx	xx	xx	xx	xx	xx
xxx	xx	ddmmyy(xx)	ddmmyy(xx)	xx	xx	xx	xx	xx	xx
xxx	xx	ddmmyy(xx)	ddmmyy(xx)	xx	xx	xx	xx	xx	xx
xxx	xx	ddmmyy(xx)	ddmmyy(xx)	xx	xx	xx	xx	xx	xx
xxx	xx	ddmmyy(xx)	ddmmyy(xx)	xx	xx	xx	xx	xx	xx

TACTILE TABLES - SAP

Sponsor: Tactile Medical Systems
Protocol: 6010

page 1 of Y

Table 14.3.3 Safety Analysis: Incidence of Ulcer-Related Adverse Events at 16 Weeks
Safety sample

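### Table 14.3.1 attaches a maximum-severity footnote to the causality rows, although SAP 8.2.1 counts each subject under the highest causality

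*SAP*

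**What the plan says.** SAP section 8.2.1 (Adverse Events) assigns the summary by severity, outcome, causality and seriousness to Table 14.3.1. For subjects with more than one event it states that "the event with the highest level of severity, outcome or causality, seriousness, respectively, will be reported". The last word of that rule ties each maximum to its own attribute: worst severity for the severity summary, strongest relationship for the causality summary.

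The shell of Table 14.3.1 in the SAP appendix carries the same marker on two block headings: "Patients with AEs by Severity ^a" and "Patients with AEs by Causality ^a". The only text for marker a is that patients "experiencing more than one adverse event are counted under the maximum severity experienced across events". No footnote gives a counting rule for causality. The Outcome block has no marker, although 8.2.1 covers outcome as well.

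The causality block has five categories (definitely, probably and possibly related, not related, no event) and one p-value cell. The table note gives the test: "P-value based on Kruskal-Wallis test controlling for stratification".

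**The concern.** Two counting rules apply to the same rows. They agree only when a subject's most severe event also has the subject's highest causality. Otherwise the footnote, read literally, takes the causality of the most severe event and leaves a milder but more strongly related event out of the block.

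Table 14.3.1 is the only summary by causality among the supplied shells. Table 14.3.2 counts by internal code and Table 14.3.3 by type of ulcer-related event, and neither shows relatedness. Mild events do reach the data, because protocol section 9.3 requires its pre-defined events, skin irritation and blistering among them, to be reported whatever their severity. The rule the programmer chooses therefore affects the related counts that a reader sees, and the test on them.

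**Working it through.** **Side by side.** Take a hypothetical subject with two events: one mild and definitely related, one severe and not related.

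| Rule | Severity row | Causality row |
|---|---|---|
| SAP 8.2.1 | Severe | Definitely related |
| Footnote a, read literally | Severe | Not related |

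**Direction.** The most severe event is one of the subject's events, so it cannot be more related than the subject's most related event. The literal footnote can move a subject only to the same or a lower causality row, in either arm and for any data.

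**Size.** The plan states no figure to reproduce and no event rates. The following is an illustration, and every input is an assumption:
- events per subject are Poisson with mean m; 30% are related (λR = 0.3m) and 70% unrelated (λU = 0.7m);
- mild/moderate/severe shares are 75/20/5% for related and 40/40/20% for unrelated events;
- when a related and an unrelated event tie for most severe, the subject counts as related;
- definitely, probably and possibly related are combined.

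Under 8.2.1, the share of subjects with a related event is 1 − exp(−λR).

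Under the literal footnote it is the sum over severity levels k of P(worst related event is level k) × P(no unrelated event is worse than k). With F(k) the cumulative severity share and F(0) = 0:

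Σ [exp(−λR(1 − FR(k))) − exp(−λR(1 − FR(k−1)))] × exp(−λU(1 − FU(k)))

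At m = 1.0:
- 8.2.1: 1 − exp(−0.3) = 25.9%
- mild: (exp(−0.075) − exp(−0.3)) × exp(−0.42) = 0.1869 × 0.6570 = 0.1228
- moderate: (exp(−0.015) − exp(−0.075)) × exp(−0.14) = 0.0574 × 0.8694 = 0.0499
- severe: (1 − exp(−0.015)) × 1 = 0.0149
- footnote: 0.1228 + 0.0499 + 0.0149 = 18.8%

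| Mean events per subject | 8.2.1 | Footnote | Gap (points) |
|---|---|---|---|
| 0.2 | 5.8% | 5.4% | 0.4 |
| 0.3 | 8.6% | 7.8% | 0.8 |
| 0.5 | 13.9% | 11.8% | 2.1 |
| 0.7 | 18.9% | 15.0% | 3.9 |
| 1.0 | 25.9% | 18.8% | 7.2 |
| 1.5 | 36.2% | 22.7% | 13.6 |

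Gaps are taken before rounding.

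**Sensitivity at m = 1.0.**
- Ties counted as unrelated: 0.1869 × exp(−0.7) + 0.0574 × exp(−0.42) + 0.0149 × exp(−0.14) = 0.0928 + 0.0377 + 0.0130 = 14.35%, a gap of 11.6 points. The footnote has no tie rule.
- One severity mix for related and unrelated events: with 50/35/15% the footnote gives 21.4% (gap 4.5 points), and with 60/30/10% it gives 21.8% (gap 4.1 points). The gap does not require related events to be milder.

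**Between arms.** Assume 0.3 related events per subject in one arm and 0.6 in the other, with 0.7 unrelated in both and the severity shares above. The first arm is the m = 1.0 case. For the second:
- 8.2.1: 1 − exp(−0.6) = 45.1%
- footnote: 0.3119 × 0.6570 + 0.1097 × 0.8694 + 0.0296 = 33.0%

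The ratio of the arms is 45.1/25.9 = 1.74 under 8.2.1 and 33.0/18.8 = 1.76 under the footnote. The difference is 19.2 points against 14.2. In this example the absolute levels and difference shrink while the ratio hardly moves.

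**The case against.** The strongest reply is that footnote a never tells anyone to report the causality of the most severe event. It counts patients under a severity, and the causality block has no severity rows, so it may simply be severity wording reused on a second heading. The only explicit causality rule is in 8.2.1, which names this table. A programmer who follows it produces correct counts. This stands, and it makes the harm conditional. It does not remove the conflict: the printed table would still carry a footnote that misdescribes its causality rows.

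The second reply concerns reach. Table 14.3.2 counts each subject once per internal code whatever the severity, so a mild skin irritation is still counted and compared by arm. Listing 16.2.7.1 shows every event with its causality. The safety endpoints in protocol section 12.3.4 are not defined by causality, and Table 14.3.3 is untouched. All of this stands; the exposure is one block of one table. However, Table 14.3.2 does not show relatedness, and the listing gives no counts or comparison.

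The third reply concerns size. Protocol section 9.2 defines adverse events narrowly and section 9.3 limits reporting to a short list plus an open category. Low event rates are therefore plausible, and at low rates the gap is under one point. This stands too.

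A reader might infer something stronger: that the plan hides device-related harm, or biases a test on the percentage of subjects with a device-related event. The documents do not support that. The shell says related without naming the device, it has no row for any related event, and its one p-value covers the whole five-category block.

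**Conclusion.** The contradiction is real and stands in the current SAP. Section 8.2.1 counts by highest causality, and the shell labels the same rows with a maximum-severity rule. If the footnote is programmed literally, related counts in the causality block of Table 14.3.1 can only be understated, and the block's Kruskal-Wallis p-value can change. If 8.2.1 is programmed, only the printed note is wrong.

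The size cannot be derived from the documents. Under the stated assumptions the understatement runs from about 0.4 points at a mean of 0.2 events per subject, through 2 at 0.5 and 7 at 1.0, to about 14 at 1.5. None of these should be quoted as an expected bias for this trial. The effect on the comparison of the arms depends on the data. The point deserves correction because this is the only causality summary among the supplied tables and the remedy is trivial.

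**What to change.** In the shell of Table 14.3.1:
- Keep footnote a on the severity block only.
- Give the causality block its own note: *Patients with more than one adverse event are counted once, under the strongest relationship across their events.* This is the rule already in SAP 8.2.1.
- Add a matching highest-level note to the Outcome block, which 8.2.1 also covers.

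The cost is a few lines in the table shell. It needs no new data and no change of method.

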Efficacy analysis and associated p-value calculation are described below and will be further elaborated in the Statistical Analysis Plan (SAP) issued prior to database lock. Statistical tests will be performed at a one-sided alpha of .025 for non-inferiority and two-sided alpha level of 0.05 for all other comparisons, unless otherwise specified. Between-group analyses will employ analysis of covariance (ANCOVA) with stratum and treatment group as covariates for continuous data, and chi-square or Cochran-Mantel Haenzel (CMH) methods for stratified categorical data. Kruskal-Wallis tests will be used to compare ordinal variables stratified by ulcer age, wound area and treatment group. If serious departures in the assumptions of normality and homogeneity of variance occur, nonparametric methods will be used for continuous data.

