#### 12.3.2 econdary Endpoints

The secondary endpoints in clinical order of prioritization are as follows:

- the difference in changes in HRQOL at 16 weeks using the overall score of the Charing Cross Venous Ulcer Questionnaire.
- outpatient cost per subject at 16 weeks

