#### 12.6 Analysis Plan:

##### 12.6.1 General Analysis Issues:

Statistical analysis will be performed using SAS Version 9.4 or higher. Non-inferiority analyses will be considered statistically significant at the

one-sided  $\alpha=.025$  level. All other p-values presented will be two-sided and will be considered statistically significant at the two-sided  $\alpha=.05$  level of significance unless otherwise noted. Statistical testing of the primary and secondary endpoints (Stage I) will be performed in hierarchical fashion. The primary efficacy analysis will be performed at the one-sided  $\alpha=.025$  level. If the primary efficacy analysis is statistically significant then the first secondary end point will be analyzed at the two-sided  $\alpha=.05$  level. If this analysis is statistically significant, then the second secondary end point will be analyzed at the two-sided  $\alpha=.05$  level. Otherwise, testing on secondary endpoints will cease and the treatment will not be considered beneficial on either secondary endpoint. P-values for exploratory endpoints will not be adjusted for multiple comparisons.

Baseline demographic and background variables will be summarized by treatment group and strata. For categorical variables, frequencies and percentages will be presented. For continuous variables, descriptive statistics including: sample size, mean, standard deviation, minimum, and maximum, will be presented. Continuous variables will be compared between treatment and control groups using ANCOVA. Categorical variables will be compared between treatment and control groups using the Kruskal-Wallis tests.

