#### 12.6.3 econdary Endpoint Analysis

The following analyses will be carried out on all three analysis populations defined above. ACTitouch® treated subjects will be compared with multi-layer bandaging treated subjects in terms of:

- the difference in changes in HRQOL at 16 weeks assessed by the overall score of the Charing Cross Venous Ulcer Questionnaire using a similar ANCOVA model as used in similar to the Primary Endpoint Analysis. If the primary efficacy analysis was significant, then the difference will be tested at the two-sided  $\alpha=.05$  level.
- the difference in VLU-related outpatient cost per subject at 16 weeks between ACTitouch® treated subjects with multi-layer bandaging treated subjects using non-parametric rank-order, Wilcoxon rank sum tests. If the prior secondary efficacy analysis was significant, then the difference will be tested at the  $\alpha=.05$  level.

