8.3.2 Secondary Efficacy Analysis

[figure not shown]
The following analyses will be carried out on all three analysis populations defined above.:

- ACTitouch® treated subjects will be compared with multi-layer bandaging treated subjects in terms of the difference in changes in HRQOL at 16 weeks assessed by the overall score of the Charing Cross Venous Ulcer Questionnaire using a similar ANCOVA model as used in similar to the Primary Endpoint Analysis. If the primary efficacy analysis was significant, then the difference will be tested at the two-sided $\alpha=0.05$ level – Table 14.2.6.

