	Median(Min,Max)	xx(xx,xx)	xx(xx,xx)	xx(xx,xx)	xx(xx,xx)		

Note: [‡]Estimates of mean difference between treatment groups, 95% confidence interval and P-value based on linear mixed model ANCOVA with the following covariates: treatment group; duration of VLU ([1,6]; (6,24] months); baseline size of VLU, [1.5,12cm], (12,50cm]; history of diabetes; age.

TACTILE TABLES - SAP

Sponsor: Tactile Medical Systems
Protocol: 6010

page 1 of Y

Table 14.2.7 Exploratory Efficacy Analysis: Ulcer Free Days at 16 Weeks
Evaluable Available Case Population

Label	Statistic	% Wound Area at Follow-up		Changes in % Wound Area from Baseline		[Treatment - Control] Difference (95% CI)*	P-Value*
		Treatment Group (N=122)	Control Group (N=128)	Treatment Group	Control Group		
baseline	N	xx	xx				
	Mean(SD)	xx.x(xx.x)	xx.x(xx.x)				
	Median(Min,Max)	xx(xx,xx)	xx(xx,xx)				
16 weeks	N	xx	xx	xx	xx		
	Mean(SD)	xx.x(xx.x)	xx.x(xx.x)	xx.x(xx.x)	xx.x(xx.x)	xx.x(xx.x, xx.x)	x.xxx
	Median(Min,Max)	xx(xx,xx)	xx(xx,xx)	xx(xx,xx)	xx(xx,xx)		

Note: *Estimates of mean difference between treatment groups, 95% confidence interval and P-value based on non-parametric ANCOVA with the following covariates: treatment group; duration of VLU ([1,6]; (6,24] months); baseline size of VLU, [1.5,12cm], (12,50cm]; history of diabetes; age.

TACTILE TABLES - SAP

Sponsor: Tactile Medical Systems
Protocol: 6010

page 1 of Y

Table 14.2.10 Exploratory Efficacy Analysis: Changes in VCSS at 16 Weeks
Evaluable Available Case Population

Label	Statistic	% Wound Area at Follow-up		Changes in % Wound Area from Baseline		[Treatment - Control] Difference (95% CI) [*]	P-Value [*]
		Treatment Group (N=122)	Control Group (N=128)	Treatment Group	Control Group		
baseline	N	xx	xx				
	Mean(SD)	xx.x(xx.x)	xx.x(xx.x)				
	Median(Min,Max)	xx(xx,xx)	xx(xx,xx)				
16 weeks	N	xx	xx	xx	xx		
	Mean(SD)	xx.x(xx.x)	xx.x(xx.x)	xx.x(xx.x)	xx.x(xx.x)	xx.x(xx.x, xx.x)	x.xxx
	Median(Min,Max)	xx(xx,xx)	xx(xx,xx)	xx(xx,xx)	xx(xx,xx)		

Note: ^{*}Estimates of mean difference between treatment groups, 95% confidence interval and P-value based on ANCOVA with the following covariates: treatment group; duration of VLU ([1,6]; (6,24] months); baseline size of VLU, [1.5,12cm], (12,50cm]; history of diabetes; age.

TACTILE TABLES - SAP

Sponsor: Tactile Medical Systems
 Protocol: 6010

page 1 of Y

Table 14.2.11. Exploratory Analysis: Cox PH Analysis of the Time to 100% Healed VLU

Variable	Hazard Rate	95% Confidence Interval		P-value

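### The first secondary endpoint, change in the Charing Cross score, is analysed without the baseline Charing Cross score as a covariate, which gives up precision on a test that gates the cost endpoint

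*SAP*

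**What the plan says.** Protocol 12.3.2 defines the first secondary endpoint as "the difference in changes in HRQOL at 16 weeks using the overall score of the Charing Cross Venous Ulcer Questionnaire". The response is therefore a change from baseline.

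The model is described in four places:

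- Protocol 12.6.3: the change is "assessed by the overall score of the Charing Cross Venous Ulcer Questionnaire using a similar ANCOVA model", with reference to the primary analysis.
- SAP 8.3.2: the comparison is made "using a similar ANCOVA model as used in similar to the Primary Endpoint Analysis".
- SAP Table 14.2.6, note: "P-value based on linear mixed model ANCOVA with the following covariates: treatment group; duration of VLU" (two classes), followed by "baseline size of VLU, [1.5,12cm], (12,50cm]; history of diabetes; age". This is the only place where the covariates for this endpoint are written out.
- Protocol 12.1, general rule: "Between-group analyses will employ analysis of covariance (ANCOVA) with stratum and treatment group as covariates for continuous data".

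None of them names the baseline Charing Cross score. The only baseline measurement in the list is ulcer size class. Table 14.2.6 has a baseline row, but for descriptive statistics only.

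Protocol 12.6.1 sets the testing order. The Charing Cross endpoint is tested at two-sided 0.05 if the primary non-inferiority test succeeds, and outpatient cost follows only if Charing Cross is significant. Otherwise "testing on secondary endpoints will cease and the treatment will not be considered beneficial on either secondary endpoint".

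**The concern.** In a change-score analysis the baseline score is usually the strongest available predictor of the change, because subjects who start with worse scores have more room to improve. Leaving it out keeps that variation in the error term. It also lets any chance difference between the arms at baseline pass into the estimated treatment effect.

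The primary model does carry a baseline form of its own outcome, namely ulcer size class. When the list was reused for the questionnaire, the ulcer-size term stayed and no questionnaire term was put beside it.

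The test carries the synopsis objective of a greater improvement in quality of life, which is a superiority claim. Under the protocol hierarchy it is also the gate to the cost claim, so avoidable noise here lowers the chance of both.

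**Working it through.** **Inputs from the documents.** 204 subjects randomised 1:1, 102 per arm (synopsis; protocol 12.1). Two-sided alpha 0.05 (protocol 12.6.1). The available text states no power, SD, correlation or expected effect for the Charing Cross score, so there is no planned figure to reproduce for this endpoint.

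**Assumptions.** Let ρ be the correlation between baseline and week-16 score, and k the week-16 SD divided by the baseline SD (baseline SD = 1). Both are read as conditional on the covariates already in the model. Grid: ρ = 0.3, 0.5, 0.7, 0.9 and k = 0.8, 1.0, 1.2, 1.3.

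**Step 1: variances.**

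- Change without baseline adjustment: Vc = 1 + k² − 2ρk
- Change with baseline as covariate: Va = k²(1 − ρ²)
- Vc − Va = (1 − ρk)² ≥ 0

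Apart from the cost of one degree of freedom, adjustment therefore cannot lose. The gain is nil only at ρk = 1.

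**Step 2: variance ratio Va/Vc.** At k = 1 it reduces to (1 + ρ)/2.

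| k | ρ=0.3 | ρ=0.5 | ρ=0.7 | ρ=0.9 |
|---|---|---|---|---|
| 0.8 | 0.50 | 0.57 | 0.63 | 0.61 |
| 1.0 | 0.65 | 0.75 | 0.85 | 0.95 |
| 1.2 | 0.76 | 0.87 | 0.97 | 0.98 |
| 1.3 | 0.81 | 0.91 | 0.99 | 0.92 |

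Worked corners:

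- k = 0.8, ρ = 0.3: Va = 0.64 × 0.91 = 0.5824 and Vc = 1 + 0.64 − 0.48 = 1.16, ratio 0.502.
- k = 1.3, ρ = 0.7: Va = 1.69 × 0.51 = 0.8619 and Vc = 1 + 1.69 − 1.82 = 0.87, ratio 0.991.

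**Step 3: power.** Suppose the planned analysis had 80% power (hypothetical). Adjusted power is Φ(2.802/√ratio − 1.960):

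- ratio 0.65, 0.75, 0.85 (k = 1): 93.5%, 89.9%, 86.0%
- grid extremes 0.502 and 0.991: 97.7% and 80.4%

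Put as sample size at k = 1, adjusting 204 subjects gives the precision of 204/0.65 = 314, 204/0.75 = 272 or 204/0.85 = 240 unadjusted subjects.

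**Step 4: chance imbalance.** The SE of the baseline difference is √(2/102) = 0.140 baseline SD. A 1-SE imbalance moves the unadjusted difference, in units of its own SE, by (1 − ρk)/√(1 + k² − 2ρk). At k = 1 this is 0.59, 0.50, 0.39 and 0.22 for ρ = 0.3, 0.5, 0.7 and 0.9.

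**Step 5: cost of adjusting.** If the baseline score explained nothing (ρk = 1), variance would rise by a factor of about 1 + 1/(204 − 4) = 1.005.

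**Simulation checks at 102 per arm.** With 20,000 runs and k = 1, the variance ratios were 0.648, 0.748, 0.860 and 0.950 across the four correlations. They were 0.993 at k = 1.3, ρ = 0.7 and 0.566 at k = 0.8, ρ = 0.5. A second simulation (2,000 runs, k = 1) put the other four covariates in the model, generated as unrelated to the score. SE ratios were 0.807, 0.867 and 0.924 at ρ = 0.3, 0.5 and 0.7, against 0.806, 0.866 and 0.922 by formula. Power rose from 79.0% to 92.7%, 79.4% to 88.5% and 79.0% to 85.0%.

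**The case against.** **The note may be copied text.** The Table 14.2.6 shell is headed with wound-area columns and shows N=122 and 128, and the same covariate list recurs under other tables. The list may therefore not be a considered decision. That is plausible, but it explains the omission without repairing it: as written, this is the list the programmer will use.

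**The text says similar, not same.** The exploratory items refer to the same covariates or method, whereas this endpoint has only a similar model. A similar model could carry the outcome's own baseline, as the primary model does. But the one explicit list does not include it, and the choice should not stay open in an open-label trial.

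**Linear mixed model.** If baseline entered as a repeated response, most of the loss would disappear. Nothing in either document says so, and the response is described as a change.

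**Abbreviated SAP.** It refers to a fuller original that may say more. That cannot be checked from the available text.

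**Consequence and size.** Three points stand. The abbreviated SAP shows no cost table, so the effect on the cost claim rests on the protocol hierarchy. With 122 and 128 subjects the imbalance figure is √(1/122 + 1/128) = 0.127 SD instead of 0.140. The magnitude is wholly assumption-based and close to nil at one corner of the grid. The loss also falls mainly on the sponsor's own claim, since the planned test does not favour the device wrongly.

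**Conclusion.** The concern holds. No visible text puts the baseline Charing Cross score into the model for change in that score, and the one explicit covariate list leaves it out. This is a matter of efficiency, not validity: the planned estimate is unbiased under randomisation and the type I error is controlled.

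Over the assumed range of ρ and k, adjustment would reduce the variance of the treatment difference by between about 1% and 50%. The direction does not depend on the assumptions, beyond the roughly 0.5% worst-case cost; only the size does. Because the test is a gated superiority test and the remedy is almost free, the change should be made, although the trial does not fail without it.

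**What to change.** Name the baseline Charing Cross overall score as a continuous covariate in SAP 8.3.2, the Table 14.2.6 note and protocol 12.6.3. Use the same pre-randomisation value from which the change is computed. Date the edit before database lock and before any unblinded comparison of this endpoint. Protocol 12.1 already foresees that the SAP will elaborate the analyses before lock.

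For consistency only, add the baseline VCSS to SAP 8.3.3 and the Table 14.2.10 note, where the list begins "P-value based on ANCOVA with the following covariates: treatment group; duration of VLU". That analysis is exploratory and gates nothing.

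The primary model needs no change on this account. The cost is a wording edit and one degree of freedom, with no new data, visits or subjects.
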